5.2 Exclusion Criteria

5.2.1 Dose Escalation Exclusion Criteria

Any potential subject who meets any of the following criteria will be excluded from participating in the trial.

1. Prior treatment with a CD37-targeting agent.
2. Prior allogeneic HSCT.
3. Autologous HSCT within 3 months before the first dose of GEN3009.
4. Criterion updated as per Amendment 5
 - 4.1 Treatment with an anti-cancer biologic including anti-CD20 therapy, radio-conjugated or toxin-conjugated antibody or chimeric antigen receptor (CAR) T cell therapy within 4 weeks or 5 half-lives, whichever is shorter, before the first dose of GEN3009. Treatment with small molecules such as BTK inhibitors, BCL2 inhibitors, or PI3K inhibitors within 5 half-lives prior to the first dose of GEN3009.
5. Chemotherapy or radiation therapy within 2 weeks of the first dose of GEN3009.
6. Criterion updated as per Amendment 5.

6.1 Treatment with an investigational drug or an invasive investigational medical device within 4 weeks or 5 half-lives, whichever is shorter, prior to the first dose of GEN3009, and at any time during the study treatment period.

7. Autoimmune disease or other diseases that require permanent or high-dose immunosuppressive therapy.

8. Received a cumulative dose of corticosteroids more than the equivalent of 250 mg of prednisone within the 2-week period before the first dose of GEN3009.

Note: Refer to Section [6.6.2](#) for steroid dosing limitations during study treatment period.

9. Has uncontrolled intercurrent illness, including but not limited to:

- Ongoing or active infection requiring intravenous antibiotics treatment at the time of enrollment or within the previous 2 weeks prior to the first dose of GEN3009
- Symptomatic congestive heart failure (grade III or IV as classified by the New York Heart Association ([NYHA])), unstable angina pectoris or cardiac arrhythmia (refer to [Appendix 2](#))
- Myocardial infarction, intracranial bleed, or stroke within the past 6 months
- Screening 12-lead electrocardiogram (ECG) showing a baseline QT interval as corrected by Fridericia's formula (QTcF) >480 msec

10. Toxicities from previous anti-cancer therapies have not resolved to baseline levels or to Grade 1 or less except for alopecia and peripheral neuropathy.

11. Primary central nervous system (CNS) lymphoma or known CNS involvement at screening.

12. Has known past or current malignancy other than inclusion diagnosis, except for:

- Cervical carcinoma of Stage 1B or less
- Non-invasive basal cell or squamous cell skin carcinoma
- Non-invasive, superficial bladder cancer
- Prostate cancer with a current PSA level <0.1 ng/mL
- Criterion deleted as per Amendment 3
- Any curable cancer with a CR of >2 years duration

13. Criterion updated per Amendment 5

14.1 Had allergic reactions to anti-CD20 or anti-CD37 monoclonal antibody treatment or intolerant to GEN3009 excipients (refer to the GEN3009 IB for more information).

14. Criterion updated per Amendment 5

14.1 Has had major surgery, (eg, requiring general anesthesia) within 4 weeks before screening or will not have fully recovered from surgery, or has major surgery planned during the time the subject is expected to participate in the trial (or within 4 weeks after the last dose of GEN3009 and/or GEN3013).

Note: Subjects with planned minor surgical procedures to be conducted under local anesthesia may participate.

15. Has known history/positive serology for hepatitis B (unless immune due to vaccination or resolved natural infection or unless passive immunization due to immunoglobulin therapy):
 - Positive test for antibodies to the hepatitis B core antigen (anti-HBc) **and**
 - Negative test for antibodies to the hepatitis B surface antigen (anti-HBs).
16. Known medical history or ongoing hepatitis C infection that has not been cured.
17. Criterion updated per Amendment 5
 - 17.1 Known history of seropositivity for HIV infection. Note: HIV testing is required at screening only if required per local health authorities or institutional standards.
18. Is a woman who is pregnant or breast-feeding, or who is planning to become pregnant while enrolled in this trial or within 12 months after the last dose of GEN3009.
19. Is a man who plans to father a child while enrolled in this trial or within 12 months after the last dose of GEN3009.
20. Criterion updated as per Amendment 5
 - 20.1 Has any condition for which, in the opinion of the investigator, participation would not be in the best interest of the subject (eg, compromise the well-being) or that could prevent, limit, or confound the protocol-specified assessments. Additionally, vulnerable subjects or subjects under guardianship, curatorship, judicial protection or deprived of liberty), are excluded from participation in this trial.
21. Prior treatment with live, attenuated vaccines within 4 weeks prior to initiation of GEN3009. Examples of live vaccines include, but are not limited to, the following: measles, mumps, rubella, varicella/zoster (chicken pox), yellow fever, rabies, Bacillus Calmette–Guérin, and typhoid vaccine. Seasonal influenza vaccines for injection are generally killed virus vaccines and are allowed; however, intranasal influenza vaccines (eg, FluMist®) are live attenuated vaccines and are not allowed. Experimental and/or non authorized SARS-CoV-2 vaccinations are not allowed.
22. Lymphomas leukemia phase: high absolute lymphocyte count or the presence of abnormal cells in the peripheral blood indicating circulating lymphoma cells.

5.2.2 Expansion (including Safety Run-in) Exclusion Criteria

Any potential subject who meets any of the following criteria will be excluded from participating in the trial.

1. Prior treatment with a CD37-targeting agent.
2. **GEN3009 + GEN3013 combination cohort only:** Prior treatment with a CD3 × CD20 bispecific antibody.
3. Prior allogeneic HSCT.
4. Autologous HSCT within 3 months before the first dose of GEN3009.
5. Lymphomas leukemia phase: high absolute lymphocyte count or the presence of abnormal cells in the peripheral blood indicating circulating lymphoma cells

6. Treatment with an anti-cancer biologic including anti-CD20 therapy, radio-conjugated or toxin-conjugated antibody or CAR T cell therapy within 4 weeks or 5 half-lives, whichever is shorter, before the first dose of GEN3009. Treatment with small molecules such as BTK inhibitors, BCL2 inhibitors, or PI3K inhibitors within 5 half-lives prior to the first dose of GEN3009.
7. Chemotherapy or radiation therapy within 2 weeks of the first dose of GEN3009.
8. Treatment with an investigational drug or an invasive investigational medical device within 4 weeks or 5 half-lives, whichever is shorter, prior to the first dose of GEN3009, and at any time during the study treatment period
9. Autoimmune disease or other diseases that require permanent or high-dose immunosuppressive therapy.
10. Received a cumulative dose of corticosteroids more than the equivalent of 250 mg of prednisone within the 2-week period before the first dose of GEN3009.

Note: Refer to Section [6.6.1](#) for steroid dosing limitations during the study treatment period.

11. Has uncontrolled intercurrent illness, including but not limited to:
 - a. Ongoing or active infection requiring intravenous antibiotics treatment at the time of enrollment or within the previous 2 weeks prior to the first dose of GEN3009 or GEN3013
 - b. Symptomatic congestive heart failure (grade III or IV as classified by the NYHA), unstable angina pectoris or cardiac arrhythmia (refer to [Appendix 2](#)) and/or known decrease ejection fraction of <45%
 - c. Myocardial infarction, intracranial bleed, or stroke within the past 6 months
 - d. Screening 12-lead ECG showing a baseline QTcF >480 msec
12. **GEN3009 + GEN3013 combination cohort only:** Seizure disorder requiring therapy (such as steroids or anti-epileptics)
13. History of severe allergic or anaphylactic reactions to monoclonal antibody therapy.
14. Toxicities from previous anti-cancer therapies have not resolved to baseline levels or to Grade 1 or less except for alopecia and peripheral neuropathy.
15. Primary CNS lymphoma or known CNS involvement at screening.
16. Has known past or current malignancy other than inclusion diagnosis, except for:
 - a. Cervical carcinoma of Stage 1B or less
 - b. Non-invasive basal cell or squamous cell skin carcinoma
 - c. Non-invasive, superficial bladder cancer
 - d. Prostate cancer with a current PSA level < 0.1 ng/mL
 - e. Any curable cancer with a CR of >2 years duration
17. Had allergic reactions to anti-CD20 or anti-CD37 monoclonal antibody treatment or intolerant to GEN3009 excipients (refer to the GEN3009 IB for more information)
18. **GEN3009 + GEN3013 combination cohort only:** Intolerant to GEN3013 excipients (refer to the GEN3013 IB for more information)

19. Has had major surgery, (eg, requiring general anesthesia) within 3 weeks before screening or will not have fully recovered from surgery, or has major surgery planned during the time the subject is expected to participate in the trial (or within 4 weeks after the last dose of GEN3009).
Note: Subjects with planned minor surgical procedures to be conducted under local anesthesia may participate.

20. Has known history/positive serology for hepatitis B (unless immune due to vaccination or resolved natural infection or unless passive immunization due to immunoglobulin therapy):

- Positive test for anti-HBc
- and
- Negative test for anti-HBs.

21. Known medical history or ongoing hepatitis C infection that has not been cured.

22. Known history of seropositivity for HIV infection. Note: HIV testing is required at screening only if required per local health authorities or institutional standards.

23. Is a woman who is pregnant or breast-feeding, or who is planning to become pregnant while enrolled in this trial or within 12 months after the last dose of GEN3009 and/or GEN3013.

24. Is a man who plans to father a child while enrolled in this trial or within 12 months after the last dose of GEN3009 and/or GEN3013.

25. Has any condition for which, in the opinion of the investigator, participation would not be in the best interest of the subject (eg, compromise the well-being) or that could prevent, limit, or confound the protocol-specified assessments. Additionally, vulnerable subjects or subjects under guardianship, curatorship, judicial protection or deprived of liberty), are excluded from participation in this trial.

26. Prior treatment with live, attenuated vaccines within 4 weeks prior to initiation of GEN3009. Examples of live vaccines include, but are not limited to, the following: measles, mumps, rubella, varicella/zoster (chicken pox), yellow fever, rabies, Bacillus Calmette–Guérin, and typhoid vaccine. Seasonal influenza vaccines for injection are generally killed virus vaccines and are allowed; however, intranasal influenza vaccines (eg, FluMist®) are live attenuated vaccines and are not allowed. Experimental and/or non-authorized SARS-CoV-2 vaccinations are not allowed.

5.3 Screen Failures

Screen failures are defined as subjects who consent to participate in the clinical trial but do not meet the protocol-defined eligibility criteria (refer to Section 5.1 and 5.2). Minimal information to be documented includes demography, reason for screening failure (eg, eligibility criteria not met, subject withdrew consent, other reasons) and any SAEs or AEs related to a trial assessment.

Individuals who do not meet the criteria for participation in this trial (screen failures) may be rescreened. The rescreening must be approved by the sponsor to ensure that the safety of the subject is not compromised. Screen failures may be rescreened only once. Subjects are required to sign a new ICF if updates have been made since signing the most recent ICF. All eligibility criteria must be re-assessed at the rescreening visit.

Previously submitted tumor biopsy samples are acceptable if obtained within 6 months prior to Cycle 1 Day 1. The following screening assessments may be used for rescreening if performed ≤ 3 weeks prior to Cycle 1 Day 1 or if approved by sponsor:

- Previously submitted FDG-PET CT, CT, or MRI scans with acquisition date ≤ 3 weeks prior to Cycle 1 Day 1. Scans that exceed the 3-week window may be used for trial enrollment with sponsor's approval.
- Screening laboratory assessments with the protocol-defined timelines as indicated in the visit assessment schedules (refer to [Table 2](#) and [Table 5](#)).

6 TREATMENT

6.1 Treatment Assignment or Randomization

6.1.1 Subject Numbering

After signing the ICF, subjects will be assigned a unique subject identification number before undergoing any screening procedure(s).

6.1.2 Treatment Assignment

This is an open-label trial; therefore, blinding of treatment will not be performed. Subjects will be assigned to a dose cohort based on slot availability.

During Dose Escalation, site personnel must contact the contract research organization (CRO) when a potential subject has been identified. If there is an available enrollment slot in any currently enrolling cohort, the site will be given approval to start the screening process. If there is no opening, the subject will be placed on a waiting list, and the site will be alerted of the next available opening either in the currently enrolling DL or at the next opened DL.

During the Expansion, subjects that meet the eligibility criteria will be assigned a subject number.

6.2 Premedication

6.2.1 Premedication in GEN3009 Monotherapy Cohorts

The purpose of premedication is to reduce the risk of IRRs. It is mandatory to premedicate subjects in the first treatment cycle with corticosteroids, antihistamines, antipyretics, and a leukotriene receptor antagonist before each infusion of GEN3009 (ie, Cycle 1 Day 1, Cycle 1 Day 8, Cycle 1 Day 15, and Cycle 1 Day 22). Premedication should be administered 30 minutes to 2 hours prior to the GEN3009 infusion:

1. Prednisolone 100 mg, or equivalent, administered IV. Only intermediate-acting and long-acting steroids are allowed (refer to [Appendix 3](#) for the equivalent).
2. Antipyretics: Acetaminophen 650 to 1000 mg PO, or equivalent.
3. Antihistamine: Diphenhydramine 25 to 50 mg IV or PO, or equivalent.
4. A leukotriene receptor antagonist: Montelukast 10 mg PO.

In addition to the corticosteroid administered on the day of the GEN3009 infusion, dexamethasone 5 mg PO is allowed at the investigator's discretion for up to 3 days prior to the day of GEN3009 infusion.

If there is no IRR or there is only Grade 1 or 2 IRR during Cycle 1, the use of corticosteroid is optional for subsequent cycles.

If there is a Grade 3 IRR during the Cycle 1, corticosteroid is required for Cycle 2 but may be at a reduced dose, ie, prednisolone at 80 mg IV. The use of corticosteroid is optional for subsequent cycles.

Premedication with antipyretics and antihistamines should be administered at all cycles. The leukotriene receptor antagonist only needs to be given in Cycle 1.

6.2.2 Premedication and CRS Prophylaxis in GEN3009 + GEN3013 Combination Cohort

Premedication (ie, corticosteroids, antihistamines, antipyretics and a leukotriene receptor antagonist) and post-infusion corticosteroids are mandatory for GEN3009 and GEN3009 + GEN3013 doses in Cycle 1 and Cycle 2 Day 1 as described in [Table 23](#). In subsequent treatment (ie., Cycle 2 Day 8 and beyond), steroid may be optional. Refer to [Appendix 3](#) for corticosteroid equivalent. The leukotriene receptor antagonist only needs to be given in Cycle 1. Premedication with antipyretics and antihistamines should be administered at all cycles.

If there is a Grade 3 IRR during Cycle 1, corticosteroid is required for Cycle 2 but may be at a reduced dose ie, prednisolone at 80 mg IV. The use of corticosteroid is optional for subsequent cycles.

If CRS \geq Grade 2 occurs following the fourth dose of epcoritamab administration (Cycle 2 Day 1 dose), premedication with corticosteroid and 3-day consecutive corticosteroid administration is recommended to continue for the rest of GEN3013 doses in Cycle 2. From Cycle 3 and onward, corticosteroid may be optional for premedication with antipyretics and antihistamines should be administered at all cycles.

Table 23 Premedication and Post-infusion Medication for GEN3009 + GEN3013 Combination

		Corticosteroids	Antihistamines	Antipyretics	Leukotriene receptor antagonist	
Cycle 1	Premedication for GEN3009	Day 1 (Predose)*	Prednisolone 100 mg IV (or equivalent)	Diphenhydramine 50 mg IV or oral (PO) or equivalent)	Acetaminophen 650 to 1000 mg PO (or equivalent)	Montelukast, 10 mg PO
	Premedication for GEN3009 + GEN3013 (priming dose at 0.16 mg)	Day 08 (Predose)*	Prednisolone 100 mg IV (or equivalent)	Diphenhydramine 50 mg IV or PO (or equivalent)	Acetaminophen 650 to 1000 mg PO (or equivalent)	Montelukast, 10 mg PO
		Day 09	Prednisolone 100 mg IV or PO (or equivalent)			
		Day 10	Prednisolone 100 mg IV or PO (or equivalent)			
	Premedication for GEN3009 + GEN3013 (intermediate dose at 0.8 mg)	Day 15 (Predose)*	Prednisolone 100 mg IV (or equivalent)	Diphenhydramine 50 mg IV or PO (or equivalent)	Acetaminophen 650 to 1000 mg PO (or equivalent)	Montelukast, 10 mg PO
		Day 16	Prednisolone 100 mg IV or PO (or equivalent)			
		Day 17	Prednisolone 100 mg IV or PO (or equivalent)			
	Premedication for GEN3009 + GEN3013 administration 48 mg)	Day 22 (Predose)*	Prednisolone 100 mg IV (or equivalent including oral dose)	Diphenhydramine 50 mg IV or PO (or equivalent)	Acetaminophen 650 to 1000 mg PO (or equivalent)	Montelukast, 10 mg PO

		Corticosteroids	Antihistamines	Antipyretics	Leukotriene receptor antagonist
		Day 23	Prednisolone 100 mg IV or PO (or equivalent)		
		Day 24	Prednisolone 100 mg IV (or equivalent including oral dose)		
Cycle 2	Premedication for GEN3009 + 4th GEN3013 administration (48 mg)	Day 1 (Predose)*	Prednisolone 100 mg IV (or equivalent)	Diphenhydramine 50 mg IV or PO (or equivalent)	Acetaminophen 650 to 1000 mg PO (or equivalent)
		Day 2	Prednisolone 100 mg IV or PO (or equivalent)		
		Day 3	Prednisolone 100 mg IV or PO (or equivalent)		
		Day 8 and beyond	If CRS \geq Grade 2 occurs following the 4th dose of epcoritamab administration (Cycle 2 Day 1 dose), premedication with corticosteroid and 3-day consecutive corticosteroid administration is recommended to continue for the rest of GEN3013 doses in Cycle 2. From Cycle 3 and onward, corticosteroid may be optional.		

* Premedication should be given 30 minutes - 1 hour prior to the trial treatment. On the days when both trial drugs are given, administer GEN3013 s.c. first, monitor the subject for 30 minutes to 1 hour, then start the GEN3009 infusion. GEN3013 will be administered prior to GEN3009.

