CRS symptoms (not limited to chills, fever, hypotension, and hypoxia)	
• The first dose of GEN3013 is a priming dose (ie, a lower dose than subsequent doses); the second dose is an intermediate dose (ie, higher than the priming dose but lower than the subsequent full-dose levels) (Section 6.4.2).• Premedication is mandatory prior to the first 4 administrations of GEN3013 and optional for later administrations (Section 6.2.2).

	
• Prophylactic corticosteroids are mandatory for 2 days following each of the first 4 weekly administrations of GEN3013; for subsequent administrations, prophylactic steroids are only necessary if CRS \geqGrade 2 occurs following the fourth GEN3013 administration (Section 6.2.2).• Hospitalization for CRS monitoring is mandatory for at least 24 hours following the third dose (first full dose) of GEN3013 administration only. A lead-in dose of GEN3009 will be given a week before GEN3009 + GEN3013 combination to reduce the potential risk of CRS with GEN3013. 
See Section 7.5.2 and Appendix 13 for supportive care and management of CRS.

ICANS	Monitoring of the neurologic and cognitive status (including, but not limited to, confusion, expressive aphasia, headache, seizures and altered level of consciousness) of subjects to secure timely introduction of supportive care (Sections 7.5.3 and 9.3.1.1 and Appendix 14)
Clinical TLS	Laboratory monitoring; prophylaxis and management guidelines (Appendix 4).

The risks to subjects treated with the GEN3009 and GEN3013 combination will be minimized by a preceding safety run-in phase to inform the tolerability of the combination treatment before opening the Expansion phase, staggered dosing among subjects within a DL, requirement for hospitalization following the third dose (first full dose) of GEN3013 treatment, and established guidelines for the recognition and management of CRS and ICANS in addition to the compliance with the eligibility criteria, trial procedures, and close monitoring and management of TEAEs.

Furthermore, aggregate safety data will be reviewed by an independent data monitoring committee (DMC) on a regular basis to ensure the benefit to risk ratio remain acceptable for trial subjects.

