7.4.2.2 GEN3013 Dose Modification Rules

Dose reduction is not allowed for GEN3013 on an individual subject level in this trial. Refer to Section [4.3](#) for dosing rationale.

If a dose is delayed more than 6 weeks, the subject should be asked to perform an unscheduled visit for collection of AEs, concomitant medications, laboratory values (including hematology, biochemistry, and coagulation values), and a limited physical examination (as clinically indicated) after consultation with the sponsor's medical monitor.

A repriming cycle is necessary if dose is delayed at certain time points, as described below. A repriming cycle consists of a weekly schedule of a priming dose, intermediate dose, and 2 full doses. Refer to [Table 15](#) for the repriming cycle Visit Assessment Schedule.

A repriming cycle should occur:

- For the second GEN3013 full dose onward (ie, C2D1), if the interval between the previous dose of GEN3013 and next planned dose exceeds 6 weeks.

During the repriming cycle, CRS prophylaxis must be resumed with 3 consecutive days of corticosteroids beginning at each GEN3013 dose, until at least 1 full dose of GEN3013 is administered without subsequent occurrence of CRS Grade ≥ 2 (see Section [6.2.2](#)).

Once the full repriming cycle is completed, the subject should resume treatment with Day 1 of the next planned cycle (subsequent to the cycle during which the dosing was delayed). For example, if the subject experiences a 7-week delay after C3D1, the subject should receive a repriming cycle, then continue treatment at C4D1. GEN3009 dose will continue as scheduled.

If GEN3013 dose is delayed, withheld, or discontinued during the combination treatment period, GEN3009 can be continued if approved by the sponsor's medical monitor.

Refer to Section [7.4.3](#) for information about dose modifications due to AEs.

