7.4.3.2 Cytokine Release Syndrome (the GEN3009 + GEN3013 Combination Cohort)

CRS has been reported with the use of GEN3013. To date, CRS is not a known/identified risk with GEN3009. Refer to Section 7.5.2 and Appendix 13 for guidelines for grading and supportive care for CRS management.

CRS must be graded according to the ASTCT grading for CRS (Lee et al., 2019).

Table 26 GEN3013 Dose Modification for Cytokine Release Syndrome (GEN3009 + GEN3013 Combination Cohort)

CRS	
ASTCT Grade	Dose Modification
Grade 1	
Hold GEN3013 (and GEN3009 if given in combination) until resolution of CRS event and treat the subject (see Appendix 13)
Grade 2	
Hold GEN3013 (and GEN3009 if given in combination) until resolution of CRS event and treat the subject.If Grade 2 or higher CRS occurs with the second full dose or beyond, administer CRS prophylaxis with the next dose until a GEN3013 dose is given without subsequent CRS (of any grade)
Grade 3 lasting less than 72 hours	
Hold GEN3013 (and GEN3009 if given in combination) until resolution of CRS event and treat the subject.Continue with the next planned GEN3013 dose at the planned date and hospitalize the subject for at least 72 hours following this GEN3013 administration.If Grade 2 or higher CRS occurs with the second full dose or beyond, administer CRS prophylaxis with the next dose until a GEN3013 dose is given without subsequent CRS (of any grade)
Grade 3 lasting longer than 72 hours	
Permanently discontinue administration of GEN3013 and treat the subject (see Appendix 13)
Grade 3, second occurrence (ie, 2 separate Grade 3 events)	
Permanently discontinue administration of GEN3013 even if each event resolved to Grade 2 within 72 hours, and treat the subject (see Appendix 13)
Grade 4 CRS	
Permanently discontinue administration of GEN3013 and treat the subject (see Appendix 13)

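### Combination cohort: Section 6.2.2 and Table 26 give different rules for steroid prophylaxis after CRS from Cycle 2 Day 1 onward, and neither is said to govern

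*Protocol*

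**What the plan says.** In the combination cohort, steroids are mandatory with every dose through Cycle 2 Day 1 (C2D1) and optional from C2D8 (Section 6.2.2, Table 23). There is one CRS-based exception. If CRS of Grade 2 or higher "occurs following the fourth dose of epcoritamab administration (Cycle 2 Day 1 dose), premedication with corticosteroid and 3-day consecutive corticosteroid administration is recommended", cover continues for the remaining Cycle 2 doses. After that, "From Cycle 3 and onward, corticosteroid may be optional".

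The CRS row of Table 16 (Section 2.3.2) covers the first four GEN3013 doses and then says "for subsequent administrations, prophylactic steroids are only necessary if CRS" of Grade 2 or higher follows the fourth administration. It cites Section 6.2.2.

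Table 26 (Section 7.4.3.2) has a different rule in two rows, Grade 2 and Grade 3 lasting less than 72 hours: "If Grade 2 or higher CRS occurs with the second full dose or beyond, administer CRS prophylaxis with the next dose". Its end point is also different: "administer CRS prophylaxis with the next dose until a GEN3013 dose is given without subsequent CRS (of any grade"). Longer Grade 3, a second Grade 3 and Grade 4 CRS all end GEN3013 permanently.

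**The concern.** The two rules start at the same dose but differ in which later events trigger cover, how firmly it is required and when it stops. A site can give steroids and satisfy both. The difficulty runs the other way: a site that follows Section 6.2.2 can leave out a step that Table 26 directs.

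At stake is the next 48 mg dose in a subject who has just had Grade 2 or short Grade 3 CRS. After Grade 2 CRS, Table 26 requires dosing to be held until the event resolves but, unlike the short Grade 3 row, does not require admission at the next dose. In regular cycles, admission is otherwise mandatory only after C1D22 (Section 6.4.2). Prophylaxis is therefore the main extra preventive step in the Grade 2 row, and Section 6.2.2 leaves it optional.

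**Working it through.** No statistical figure is involved, so the check compares the texts and counts scheduled doses.

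**1. Same starting dose.** From Table 21, GEN3013 is given on C1D8 (dose 1), C1D15 (dose 2), C1D22 (dose 3, first full dose) and C2D1 (dose 4, second full dose). Section 7.4.2.2 agrees: "For the second GEN3013 full dose onward (ie, C2D1"). The fourth dose in Section 6.2.2 and the second full dose in Table 26 are the same.

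**2. Side by side, regular cycles.**

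| | Section 6.2.2 / Table 23 | Table 26 |
|---|---|---|
| Trigger | Grade 2 or higher CRS after C2D1 | Grade 2, or Grade 3 under 72 hours, at C2D1 or any later dose |
| Strength | Recommended | Directed |
| Cover ends | After the last Cycle 2 dose | After a dose with no CRS of any grade |
| Cycle limit | Optional from Cycle 3 | None |
| Regimen | Prednisolone 100 mg on 3 consecutive days | Not stated |

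**3. Cases.**
- Grade 2 CRS at C2D1, then a CRS-free C2D8: Table 26 directs cover at C2D8 and stops. Section 6.2.2 recommends cover at C2D8, C2D15 and C2D22. Here Section 6.2.2 is the longer rule, though the weaker one.
- First Grade 2 CRS at C2D15: Table 26 directs cover at C2D22. Section 6.2.2 has no trigger.
- First Grade 2 CRS at C3D1: Table 26 directs cover at C3D8. Under Section 6.2.2 steroids are optional.
- Second Grade 3 event: "Permanently discontinue administration of GEN3013 even if each event resolved to Grade 2 within 72 hours". No prophylaxis question arises, nor does it after longer Grade 3 or Grade 4 CRS.

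**4. Dose counts.** Planned GEN3013 doses from C2D1 to C12D1 are 4 (Cycle 2) + 4 (Cycle 3) + 9 (Cycles 4 to 12) = 17, leaving out optional Cycle 13 onward.
- Trigger doses as written: 1 for Section 6.2.2, 17 for Table 26.
- Counting only events with another planned dose to follow by C12D1: Table 26 has 17 − 1 = 16. Section 6.2.2 has 1 as written, or 3 on its most generous reading (C2D1, C2D8, C2D15).
- Gap: 16 − 3 = 13 to 16 − 1 = 15 doses.
- The last dose for which Section 6.2.2 recommends cover is C2D22, the 3 + 4 = 7th. Table 26 can reach C12D1, the 3 + 17 = 20th, and beyond.

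These are calendar doses, not a measure of risk.

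**5. Which text a site reaches.** The Table 11 row for premedication and CRS prophylaxis cites Section 6.2 only. Section 6.2.2 does not mention Table 26. Section 7.4.3, which contains Table 26, sends the reader to Section 6.2.2 for premedication. Sections 6.4.2 and 6.6.1 point to Section 7 and Section 7.4.3 only in general terms.

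**6. The course itself.** Table 26 gives no drug, dose or length. Section 6.2.2 uses 3 days. For repriming cycles, Section 7.4.2.2 says 3 days and Table 15 footnote f says 4.

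**7. Effect on dose decisions.** The DLT window is Days 1 to 28. C2D1 is Day 29, so both rules act after it.

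**The case against.** The strongest reply is that nothing conflicts. Section 6.2.2 gives the routine schedule and a permission; Table 26 adds a specific instruction once CRS has occurred. Both can be followed, and the specific instruction would naturally prevail. The hold rule sits in the same Table 26 row as the prophylaxis instruction, so a site managing CRS should see both. The pointer from Section 7.4.3 to Section 6.2.2 can be read as supplying the missing regimen, and the 4-day course belongs only to repriming. Table 16 is a benefit-risk summary, and its wording alone could mean any time after dose 4.

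Much of this stands. The texts are compatible, the 3-day course is the likely intention, and the dose counts say nothing about how often the problem would arise. Other safeguards also remain: dosing is held until CRS resolves, tocilizumab must be on site (Section 6.6.1), and after short Grade 3 CRS the site must "hospitalize the subject for at least 72 hours following this GEN3013 administration" at the next dose.

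The gap remains. CRS may have resolved before the next dose is due, so the hold rule does not ensure that the site returns to Table 26 when preparing that dose. The section cited for prophylaxis then tells it that steroids are optional. Table 16 does not help, because it cites Section 6.2.2, which ties the trigger to the C2D1 dose.

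**Conclusion.** The point holds. For regular cycles the protocol has two different rules for CRS steroid prophylaxis from C2D1 onward, with no statement of which governs, and the one the visit schedule cites is narrower and weaker. The sponsor should correct it as a safety instruction. It is not a statistical defect: no DLT decision, CR rate or other planned result changes.

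The cohort is 20 + 6 = 26 to 20 + 12 = 32 subjects. Only those with Grade 2 or short Grade 3 CRS from C2D1 onward are affected. The documents give no rate for such events, so the expected number cannot be given. The conclusion rests on the texts as written, with C2D1 as both the fourth GEN3013 dose and the second full dose.

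**What to change.** - In Section 6.2.2, Table 23 and Table 16, state that after Grade 2 CRS, or a first Grade 3 CRS shorter than 72 hours, with any GEN3013 dose from C2D1 on and in any cycle, steroid prophylaxis accompanies each following GEN3013 dose until one passes with no CRS of any grade. Cross-refer to Table 26, including its discontinuation rows.
- In Table 26, state that this prophylaxis is the 3-day course of Section 6.2.2.
- The recommendation to cover the rest of Cycle 2 after CRS at C2D1 can stay as an addition.
- Two small clarifications can go in the same amendment. Section 6.3 and Table 24 send all patients to Section 6.2.1, the monotherapy text, and should add Section 6.2.2 for this cohort. Section 6.2.2 should say whether the 80 mg option after a Grade 3 infusion-related reaction applies at C2D1, where Table 23 gives 100 mg.

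The cost is amendment wording and possibly a few short steroid courses in affected subjects. At Table 23's 100 mg a day, one course is 3 × 100 = 300 mg prednisolone; the 4-day repriming form would be 4 × 100 = 400 mg. Both figures are assumptions, since Table 26 states neither dose nor length. No visits or tests are added. The steroid limit in Section 6.6.2 already exempts premedication and CRS management, so no new conflict arises.
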